Intervention:	Peer recovery coaching (PRC) to improve linkage to HIV prevention in the form of HIV pre-exposure prophylaxis (PrEP) and hepatitis C (HCV) treatment.
Objectives:	Our goal is to determine if a peer recovery coaching intervention will help patients initiate HIV prevention in the form of HIV pre-exposure prophylaxis (PrEP), HCV treatment and substance use disorder (SUD) treatment.
Design/Methodology:	Participants who consent will work one-on-one with a peer recovery coach who will provide support and linkage to various HIV, HCV and SUD resources.
Total Study Duration:	Time from initial enrollment until completion of data analysis= 12 months
Subject Participation Duration:	Time it will take to conduct the study for each individual participant =6 months

3 Background/Rationale & Purpose

3.1 Background Information

The U.S. opioid epidemic is associated with a surge in human immunodeficiency (HIV) and hepatitis C virus (HCV) infections among persons who inject drugs (PWID).^{1, 2} HIV pre-exposure prophylaxis (PrEP) and HCV curative therapy are evidence-based interventions that are recommended for PWID to prevent HIV and HCV transmission, respectively.^{3, 4} These evidence-based tools have, however, not been widely adopted in

H-39712: Peer Recovery Coaching for Infectious Diseases and Opioid Use Disorder
Version 1.1 07/07/2020

real-world settings where individuals at-risk access care.⁵ We have published studies on models of care to improve outcomes related to infectious complications of substance use such as HIV and HCV. In terms of HIV prevention, we determined in a survey of individuals admitted to a drug detoxification center that participants had limited knowledge of HIV PrEP, but expressed interest in this biomedical prevention method.⁶ As for our work related to HCV, we demonstrated that the majority of individuals with substance use disorder tested for HCV at a drug detoxification center do not link to HCV care and that active substance use was a major barrier to accessing curative HCV therapy.^{7,8} Participants also reported the need for walk-in high-touch care to assist with navigation along the HCV continuum of care. In addition to our work related to HIV and HCV care, members of our team have also shown that a peer-delivered brief motivational intervention was effective in assisting individuals to abstain from heroin and/or cocaine use.⁹ This intervention delivered by non-professionals who are themselves in recovery has been widely replicated around the country to address substance use; however, little is known about its potential role in improving HIV and HCV outcomes among individuals with opioid use disorder.

Our long-term goal is to improve HIV and HCV prevention and treatment outcomes among at-risk individuals with history of substance use. The goal of the current proposal is to determine the efficacy of a brief motivational peer recovery coaching (PRC) intervention to improve infectious diseases (HIV/HCV) prevention and care alongside substance use disorder (SUD) management for PWID. PRC will bridge the gap between professional assistance in clinical settings and sustainable recovery in the community. Our multisite study will be performed at low-barrier BMC FASTER PATHS bridge clinic (the Boston Medical Center Faster Paths walk-in bridge clinic) which links individuals with SUD to evidence-based addiction treatment such as buprenorphine and methadone.¹⁰ Bridge clinics have been especially valuable for engaging individuals who do not always feel comfortable in traditional clinical settings. The central hypothesis of the current study is that a PRC intervention will be effective in improving HIV, HCV and substance use outcomes.

Potential risks associated with participation in the study include risk associated with discussing issues related to HIV, HCV or substance use disorder and risk of breach in confidentiality. Related to emotional risk, if any participant were to experience any distress we will remind him/her of his/her right to decline answering any questions. In terms of risk of breach in confidentiality, the research staff will be trained in the importance of assuring confidentiality in record keeping. In addition, all documents will be kept in locked cabinets and computers will be password protected. In addition, the study will be conducted in compliance with the protocol, applicable regulatory

H-39712: Peer Recovery Coaching for Infectious Diseases and Opioid Use Disorder
Version 1.1 07/07/2020

requirements, and BMC/BU Medical Campus Human Research Protection policies and procedures.

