4.1 Study Objectives

The goal of the current proposal is to determine the feasibility and acceptability of a peer recovery coaching (PRC) intervention to improve infectious diseases (HIV/HCV) prevention and care alongside treatment for opioid use disorder.

Aim 1: To implement a pilot peer recovery coaching intervention at a walk-in low-barrier bridge clinic to increase uptake of a comprehensive intervention for HIV PrEP, HCV and substance use treatment among PWID accessing care at Boston Medical Center (BMC).

Aim 2: To determine the feasibility and acceptability of a combined PrEP, HCV and substance use treatment intervention at the BMC FASTER PATHS bridge clinic

We hypothesize that the peer recovery coaching intervention will facilitate both access to PrEP, HCV treatment and sustained engagement with treatment for opioid use disorder among participants. The primary outcome is patient satisfaction as a measure of the intervention's acceptability. Secondary outcomes will include (1) the proportion of patients with linkage to PrEP and treatment initiation within 3 months; (2) the proportion of patients with HCV treatment initiation within 3 months; (3) the proportion of patients with sustained linkage to opioid use treatment within 3 months (follow-up with at least one subsequent visit after the initial prescription for medication for opioid use disorder).

H-39712: Peer Recovery Coaching for Infectious Diseases and Opioid Use Disorder
Version 1.1 07/07/2020

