4.1.2 Secondary Outcome Measures

Secondary outcomes will include the following:

- (1) The proportion of participants with linkage to care.
- (2) The proportion of participants retained in care
- (3) The following additional outcomes:

HIV PrEP-related outcomes: Testing for sexually transmitted diseases including HIV, gonorrhea, chlamydia, syphilis, and hepatitis B and C.

HCV continuum of care outcomes: HCV RNA testing, liver fibrosis staging, treatment initiation and cure.

Opioid use disorder treatment-related outcomes: The proportion of individuals with repeat MOUD clinic visits and/or repeat prescriptions for opioid use disorder including buprenorphine and naltrexone, or linked to methadone treatment.

5 Study Design

The study is prospective open pilot study (N=40).

We will include 40 persons with a history of substance use recruited from the BMC FASTER PATHS bridge clinic, a facility caring for approximately 500 unique patients annually. The BMC FASTER PATHS bridge clinic provides universal HIV and HCV testing at the initial clinic intake. After reactive HCV testing, patients are linked to care at the BMC General Internal Medicine (GIM) primary care clinic.

The goal of the current study is to determine feasibility and acceptability of a peer recovery coaching intervention to improve the uptake of HIV prevention, HCV treatment

H-39712: Peer Recovery Coaching for Infectious Diseases and Opioid Use Disorder
Version 1.1 07/07/2020

and substance use treatment at a low-barrier bridge clinic. Along with the research assistant, the peer recovery coach is part of the research staff. The peer recovery coach will carry out the intervention (ie. use motivational interviewing to help participants address their history of opioid use while also accessing treatment for hepatitis C and HIV prevention methods). The peer recovery coach will carry out a baseline motivational interviewing intervention with participants and they will continue to follow the participants over a 6-month time frame. Frequency of follow-up calls will vary depending on the participant's need. The recovery coach will initially start with weekly calls.

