12.2 Sample Size Determination

H-39712: Peer Recovery Coaching for Infectious Diseases and Opioid Use Disorder
Version 1.1 07/07/2020

Given the small sample size, we are not powered to show efficacy, but we will use findings to estimate the effect size for a future efficacy trial.

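### Section 3.1 sets an efficacy goal and hypothesis, and the synopsis an effect-type goal, that conflict with the feasibility and acceptability objectives and with the protocol's own power statement

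*Combined protocol and SAP*

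**What the plan says.** The protocol gives its purpose in several places, and they do not agree.

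- **Synopsis.** "Our goal is to determine if a peer recovery coaching intervention will help patients initiate HIV prevention", and likewise HCV and substance use treatment. This is a question about effect.
- **Section 3.1.** "The goal of the current proposal is to determine the efficacy of a brief motivational peer recovery coaching (PRC) intervention". The same paragraph continues: "The central hypothesis of the current study is that a PRC intervention will be effective in improving HIV, HCV and substance use outcomes".
- **Section 4.1, repeated in 12.1.** "The goal of the current proposal is to determine the feasibility and acceptability of a peer recovery coaching (PRC) intervention". Both sections also carry a directional hypothesis: "We hypothesize that the peer recovery coaching intervention will facilitate both access to PrEP, HCV treatment and sustained engagement" with opioid use disorder treatment.
- **Primary outcome (4.1, 4.1.1, 12.1, 12.3).** "The primary outcome is patient satisfaction as a measure of" the intervention's acceptability.
- **Design (section 5).** "The study is prospective open pilot study (N=40"). The synopsis has consenting participants work one-on-one with a coach.
- **Section 12.2.** "we are not powered to show efficacy". The findings are to supply an effect size for a later efficacy trial.
- **Section 12.3.** A Wilcoxon comparison of Likert scores between two groups is planned. The secondary outcomes are to be compared with a group receiving current practice, descriptively and without a test.

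**The concern.** The goal sentences in 3.1 and 4.1 begin with the same words and end in different purposes. The one in 3.1 cannot be read as a remark about the wider research programme, because the paragraph gives the long-term goal separately in the sentence before.

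What is at stake is what the trial may conclude. With an efficacy goal and an effectiveness hypothesis on record, a favourable linkage or treatment-initiation proportion could be reported as supporting them. That inference would be weak here. Section 3.1 says the clinic already links patients to addiction treatment. Sections 5 and 9 say that participants with reactive HCV tests are linked to general internal medicine care, and they do not make this depend on coaching. Some linkage is therefore expected without the coach.

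**Working it through.** **1. Does any part of the design address the goal in 3.1?**

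| Element | What it serves | Where |
|---|---|---|
| Primary outcome: satisfaction | Acceptability | 4.1, 4.1.1, 12.1, 12.3 |
| Open pilot, N=40, coached | Feasibility | Synopsis, 4.1.1, 5 |
| Secondary outcomes: linkage, retention, initiation | Would carry the efficacy question | 4.1, 4.1.2, 12.1 |
| Analysis of those outcomes | Descriptive, no test | 12.3 |
| Power | Disclaimed for efficacy | 12.2 |

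The outcomes that bear on efficacy are secondary, and none is tested. The only named test, the Wilcoxon, concerns Likert scores. No planned analysis tests the central hypothesis of 3.1 or the directional hypothesis of 4.1 and 12.1.

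**2. Is there a comparator?** The synopsis, 4.1.1 and 5 describe one coached group, and no section describes recruiting or allocating a control. Section 12.3 refers to two groups. The documents conflict, and the second group has no definition, size or source.

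**3. The plan's own figure.** N=40 cannot be reproduced. The documents give no alpha, power, effect size, expected rate or dropout.

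**4. Precision of one proportion at n=40.** The observed rates below are assumptions, since the documents give none. The exact (Clopper-Pearson) 95% limits for x successes out of n are:

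- lower = 0.025 quantile of Beta(x, n − x + 1)
- upper = 0.975 quantile of Beta(x + 1, n − x)

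| Assumed observed | x/40 | Lower | Upper |
|---|---|---|---|
| 10% | 4 | 2.8% | 23.7% |
| 25% | 10 | 12.7% | 41.2% |
| 50% | 20 | 33.8% | 66.2% |

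**5. If a second group did exist.** Take an assumed 20-point difference and two-sided alpha 0.05, with group sizes of 20 (40 split in two) or 40 (a second group of equal size). Power = Φ[(d − 1.96·se0)/se1], where d is the difference, se0 = √[p̄(1 − p̄)·2/n], se1 = √{[p1(1 − p1) + p2(1 − p2)]/n} and p̄ is the mean of p1 and p2.

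For 30% against 50% with n=20 per group: se0 = √(0.24 × 0.1) = 0.155, se1 = √(0.46/20) = 0.152, and power = Φ[(0.2 − 1.96 × 0.155)/0.152] = Φ(−0.68), about 25%.

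| Assumed rates | Power, 20 per group | Power, 40 per group | n per group for 80% |
|---|---|---|---|
| 10% v 30% | 35% | 61% | 62 |
| 25% v 45% | 26% | 47% | 89 |
| 30% v 50% | 25% | 45% | 93 |
| 40% v 60% | 24% | 43% | 97 |

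This agrees with the statement in 12.2.

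**The case against.** The strongest reply is that the sections governing conduct and analysis already say the right thing. Satisfaction is primary, the study is called a pilot, 12.2 disclaims power for efficacy, and 12.3 leaves the linkage outcomes untested. Someone working from the statistical plan would find no efficacy test on linkage. This stands, and it limits the harm. It does not remove the conflict, because the synopsis and background are often read first and 3.1 speaks of the current study.

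A second reply is that a pilot may state the directional hypothesis that a later trial will test. That also stands. The hypothesis in 4.1 and 12.1 need not be deleted, provided the protocol says it is not tested here.

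A reader might infer four stronger things that the documents do not support:

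- **That the synopsis states an efficacy hypothesis.** It has an effect-type goal, no hypothesis, and does not use the word efficacy. The explicit efficacy goal and effectiveness hypothesis are in 3.1 only.
- **That there is flatly no comparator, so no effect could be estimated.** Section 12.3 names a second group. The supportable statement is conditional: unless that group is defined, a coach effect cannot be separated from usual linkage.
- **That the protocol declares efficacy impossible to show.** Section 12.2 says only that the study lacks the power, which is weaker.
- **That N=40 is wrong.** It has no stated derivation, but nothing here shows it is unsuitable for a feasibility study.

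**Conclusion.** The point holds. The efficacy goal and hypothesis in 3.1, and the effect-type goal in the synopsis, conflict with the objectives in 4.1 and 12.1, the satisfaction primary outcome and the power statement in 12.2. The contradiction rests on the text and needs no numerical assumption.

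The consequence for interpretation is conditional on the comparator named in 12.3 remaining undefined. In that case, the linkage and initiation proportions describe coached participants and do not measure what coaching adds. The intervals and power figures rest on assumed rates. They illustrate the limits of 40 participants and do not measure the size of the contradiction.

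**What to change.** 1. In the synopsis and 3.1, replace the effect and efficacy wording, including the central hypothesis in 3.1, with the feasibility and acceptability goal of 4.1.
2. In both 4.1 and 12.1, say that the directional hypothesis on access and engagement is for a future trial and is not tested here. Changing only one copy would create a new mismatch.
3. In 12.3, report linkage and initiation proportions among coached participants descriptively, with exact 95% confidence intervals.
4. State that no efficacy conclusion will be drawn.
5. Reconcile the two-group comparison in 12.3, and the plan in 12.2 to estimate an effect size, with the single-group design. A single group can supply a coached-group rate for planning, but not a between-group effect.

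The cost is wording only, and the stated goal becomes more modest. Sample size, procedures and data collection stay as they are. This assumes that the single-group design is kept.

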3.2 Rationale and Purpose

The U.S. opioid epidemic is associated with a surge in human immunodeficiency (HIV) and hepatitis C virus (HCV) infections among persons who inject drugs (PWID). HIV pre-exposure prophylaxis (PrEP) and HCV curative therapy are evidence-based tools that are recommended for PWID. These evidence-based measures have, however, not been widely adopted in real-world settings. A peer-delivered brief motivational intervention was shown to be effective in assisting individuals to abstain from heroin and/or cocaine use, but little is known about its potential role in improving HIV and/or HCV-related outcomes among individuals with opioid use disorder.

4 Objectives

4.1 Study Objectives

The goal of the current proposal is to determine the feasibility and acceptability of a peer recovery coaching (PRC) intervention to improve infectious diseases (HIV/HCV) prevention and care alongside treatment for opioid use disorder.

Aim 1: To implement a pilot peer recovery coaching intervention at a walk-in low-barrier bridge clinic to increase uptake of a comprehensive intervention for HIV PrEP, HCV and substance use treatment among PWID accessing care at Boston Medical Center (BMC).

Aim 2: To determine the feasibility and acceptability of a combined PrEP, HCV and substance use treatment intervention at the BMC FASTER PATHS bridge clinic

We hypothesize that the peer recovery coaching intervention will facilitate both access to PrEP, HCV treatment and sustained engagement with treatment for opioid use disorder among participants. The primary outcome is patient satisfaction as a measure of the intervention's acceptability. Secondary outcomes will include (1) the proportion of patients with linkage to PrEP and treatment initiation within 3 months; (2) the proportion of patients with HCV treatment initiation within 3 months; (3) the proportion of patients with sustained linkage to opioid use treatment within 3 months (follow-up with at least one subsequent visit after the initial prescription for medication for opioid use disorder).

H-39712: Peer Recovery Coaching for Infectious Diseases and Opioid Use Disorder
Version 1.1 07/07/2020

4.1.1 Primary Outcome Measures

This is an open pilot study. The Primary outcome will include patient satisfaction as a measure of the peer recovery coach intervention's acceptability.

4.1.2 Secondary Outcome Measures

Secondary outcomes will include the following:

- (1) The proportion of participants with linkage to care.
- (2) The proportion of participants retained in care
- (3) The following additional outcomes:

HIV PrEP-related outcomes: Testing for sexually transmitted diseases including HIV, gonorrhea, chlamydia, syphilis, and hepatitis B and C.

HCV continuum of care outcomes: HCV RNA testing, liver fibrosis staging, treatment initiation and cure.

Opioid use disorder treatment-related outcomes: The proportion of individuals with repeat MOUD clinic visits and/or repeat prescriptions for opioid use disorder including buprenorphine and naltrexone, or linked to methadone treatment.

5 Study Design

The study is prospective open pilot study (N=40).

We will include 40 persons with a history of substance use recruited from the BMC FASTER PATHS bridge clinic, a facility caring for approximately 500 unique patients annually. The BMC FASTER PATHS bridge clinic provides universal HIV and HCV testing at the initial clinic intake. After reactive HCV testing, patients are linked to care at the BMC General Internal Medicine (GIM) primary care clinic.

The goal of the current study is to determine feasibility and acceptability of a peer recovery coaching intervention to improve the uptake of HIV prevention, HCV treatment

H-39712: Peer Recovery Coaching for Infectious Diseases and Opioid Use Disorder
Version 1.1 07/07/2020

and substance use treatment at a low-barrier bridge clinic. Along with the research assistant, the peer recovery coach is part of the research staff. The peer recovery coach will carry out the intervention (ie. use motivational interviewing to help participants address their history of opioid use while also accessing treatment for hepatitis C and HIV prevention methods). The peer recovery coach will carry out a baseline motivational interviewing intervention with participants and they will continue to follow the participants over a 6-month time frame. Frequency of follow-up calls will vary depending on the participant's need. The recovery coach will initially start with weekly calls.

As part of this study, we are partnering with [name], the PI for project RECOVER (Referral, Engagement, Case Management, and Overdose Prevention Education in Recovery), an HHS-funded study using peer recovery coaching to support individuals in recovery. [name] is part of the General Internal Medicine section at BMC and he has experiences training recovery coaches for HHS-funded grant. He is a co-investigator on the current proposal. The project RECOVER team will provide assistance with hiring and training recovery coaches. Recovery coach training will involve the following topics related to substance use: (1) Addiction 101 for recovery coaches; (2) Ethical considerations for recovery coaches; (3) Mental wellness and recovery coaching; (4) Cultural competency for recovery coaches; (5) Motivational interviewing for recovery coaches. In addition to the substance use related topics, we will also add information about HIV natural history, HIV prevention methods, PrEP efficacy studies, PrEP eligibility and medical management.

The research assistant will be in charge of all the regulatory aspects of the research, recruitment (eg. approaching and consenting participants) and carrying out the baseline interviews to obtain demographic information. The research assistant will also review the participant's electronic medical records to abstract information on key outcomes measures such as linkage to substance use care, HCV treatment or HIV prevention.

- Recruitment: Participants will be recruited through flyers posted at the LBA walk-in clinic and brief information provided at intake.
 - Flyers advertising the study will be placed in the waiting and common areas of the BMC FASTER PATHS bridge clinic.
- Flyers advertising the study will be placed in the waiting and common areas of the BMC Faster Paths walk-in clinic. Patients will be approached for participation

H-39712: Peer Recovery Coaching for Infectious Diseases and Opioid Use Disorder
Version 1.1 07/07/2020

after the medical provider has explained the study at length. Some participants will reach out to our study staff through flyer contact information, while other participants will be pre-screened by medical providers and referred to the RA. Using an electronic medical record (EMR), the RA will notify the medical provider prior to the visit so proper handoff can be made. Once the RA has initiated contact with interested participant, the RA will provide a description of the study including its objectives and will provide adequate time for participants to ask questions and address concerns. Risks and benefits of the study will be discussed and interested individuals will be reminded that participation is voluntary. The RA will emphasize that participation in the study will not impact the care received at the Faster Paths clinic and that individuals may withdraw from the study at any time. Those who wish to be involved with the study will provide informed consent. The RA will obtain reason for refusal if approached individuals are not interested in participating in the study. After reactive HCV testing at the BMC Faster Paths walk-in clinic, all participants will be linked to care at the BMC General Internal Medicine (GIM) clinic.

6 Potential Risks and Benefits

